9. STUDY MANAGEMENT	15
10. PUBLICATION POLICY	15
11. REFERENCES.....	15
12. Appendices	16
Appendix 1. Summary of investigations, treatment and assessments.....	17
Appendix 2. Participant information sheet.....	17
Appendix 3. Consent form	17
Appendix 4. GP letter.....	17
Appendix 5. Participant invite letter.....	17
Appendix 6. Questionnaire to measure awareness of hypoglycaemia (Gold)	17
Appendix 7. Questionnaire to measure Hypoglycaemia fear (HFS-II)	17
Appendix 8. Questionnaire to measure general quality of life (WHOQoLBref).....	17
Appendix 9. Questionnaire to measure Diabetes distress (DDS)	17
Appendix 10. Questionnaire to measure Diabetes QoL (DQOL).....	18

STUDY SUMMARY

TITLE A Study of Flat and Circadian Insulin infusion Rates in Continuous Subcutaneous Insulin Infusion (CSII) in Adults with Type 1 Diabetes

DESIGN Randomised controlled trial

AIMS To contribute to the evidence base for the optimal initial insulin profile for adults with type 1 diabetes commencing insulin pump therapy.

OUTCOME MEASURES

[figure not shown]
- Absolute change in insulin basal rate over 24 hours after 3 rounds of basal rate testing (calculated by the sum of absolute changes for each 1 hour block compared with baseline)
- Healthcare professional time spent with subject
- Mean sensor glucose from continuous glucose monitoring after 3 rounds of basal rate testing
- Mean sensor glucose from continuous glucose monitoring after 1 round of basal rate testing
- Number of healthcare professional contacts
- CGM outcomes
- Severe hypoglycaemia
- Insulin outcomes
- Healthcare professional qualitative feedback

POPULATION People with Type 1 Diabetes commencing CSII

ELIGIBILITY Participants identified in type 1 diabetes clinics in Imperial College Healthcare NHS Trust

DURATION 4 weeks plus 1 week pre-randomisation assessment

REFERENCE DIAGRAM

1. INTRODUCTION

1.1 BACKGROUND

Initiation of insulin pump therapy in people with type 1 diabetes requires conversion of a basal insulin dose, given as once or twice daily long-acting insulin, to a continuous basal infusion regimen. This conversion may be based on basal insulin dose only, or total daily insulin dose, and may result in a flat basal insulin profile or an initial variable basal rate.

Initial variable basal rates aim to replicate circadian changes in insulin requirements and are derived from total basal insulin in adults over 24 years old, and from weight in adults aged 18 to 24 years. Initial rates were developed from 63 well-controlled people with type 1 diabetes over 14 years of age and have been assessed against a flat basal rate in a small randomised controlled trial with 12 participants. Mean glucose was lower in the circadian basal rate group with particular differences noted in the early morning when glucose rises were more pronounced in the flat basal rate group¹.

In 50 people with type 1 diabetes treated with insulin pump therapy, HbA1c was lower in those with lower basal rates at midnight, and in those with higher basal rates in the afternoon, suggesting a benefit of circadian patterns². In 33 people with type 1 diabetes over 16 years of age basal rate distribution established at commencement of pump therapy did not alter over 6 months³. However, a 6 month cross-over study of circadian rates and oligophasic basal rates showed no difference in HbA1c⁴.

Following initiation on insulin pump therapy basal rates are personalised to capillary blood and continuous interstitial fluid glucose monitoring.

In adults with type 1 diabetes starting insulin pump therapy there are limited data to guide the optimal insulin profile to rapidly achieve target glucose and minimise healthcare professional input.

1.2 RATIONALE FOR CURRENT STUDY

Hypothesis: Circadian insulin infusion rates in CSII naïve people with type 1 diabetes are closer to optimal basal rates, compared with a flat initial rate

2. STUDY OBJECTIVES

Objective: To contribute to the evidence base for the optimal initial insulin profile for adults with type 1 diabetes commencing insulin pump therapy.

3. STUDY DESIGN

Type of study: Randomised controlled trial

Duration: 4 week trial with 1 week pre-randomisation assessment

FIRST1D protocol v1.7 23.2.18
IRAS ID: 237129

Number and type of subjects:

16 participants with type 1 diabetes referred for CSII, randomised 1:1 to circadian insulin infusion rates or flat rates.

Recruitment will be undertaken in the T1DM clinics at Imperial College Healthcare NHS Trust. Participant information sheets will be given to potential subjects who have been assessed and screened for insulin pump therapy, either in person in clinic, or via post with a participant invitation letter. After a minimum of 24 hours and following any questions, informed consent will be taken.

3.1 STUDY OUTCOME MEASURES**Primary outcome:**

- Absolute change in insulin basal rate over 24 hours after 3 rounds of basal rate testing (calculated by the sum of absolute changes for each 1 hour block compared with baseline)

Secondary outcomes:

- Healthcare professional time spent with subject
- Mean sensor glucose from continuous glucose monitoring after 3 rounds of basal rate testing
- Mean sensor glucose from continuous glucose monitoring after 1 round of basal rate testing
- Number of healthcare professional contacts
- CGM outcomes
 - %time in hypoglycaemia (<2.8mmol/L)
 - %time in hypoglycaemia (<3.3mmol/L)
 - %time in hypoglycaemia (<3.9mmol/L)
 - %time in target (3.9-10mmol/L)
 - %time spent in hyperglycaemia (>10mmol/L)
 - Measures of glycaemic variability
 - Mean glucose
 - Glucose SD
- Severe hypoglycaemia
- Insulin outcomes
 - Number of insulin time blocks changed
 - Number of insulin basal rate changes
 - Change to total daily insulin dose
- Basal insulin:bolus insulin ratio
- Healthcare professional qualitative feedback

4. PARTICIPANT ENTRY**4.1 PRE-REGISTRATION EVALUATIONS**

- HbA1c
- Serum C-peptide
- Plasma glucose
- Coeliac screen

- Gastroparesis screen
- Thyroid function tests
- GOLD hypoglycaemia score

4.2 INCLUSION CRITERIA

- Adults ≥ 18 years of age
- Diagnosis of T1DM for > 1 year
- On MDI with decision made to commence CSII
- Structured education in previous 3 years
- HbA1c ≤ 75 mmol/mol (9%)
- Stimulated c-peptide < 200 pmol/L
- No severe hypoglycaemia (defined as needing 3rd party assistance) in previous year

4.3 EXCLUSION CRITERIA

- Previous CSII
- Night or shift worker
- Recurrent severe hypoglycaemia
- Pregnant or planning pregnancy
- Breastfeeding
- Enrolled in other clinical trials
- Have active malignancy or under investigation for malignancy
- Addison's Disease
- Gastroparesis
- Autonomic neuropathy
- Concomitant use of GLP-1 analogues and gliptins
- Visual impairment
- Reduced manual dexterity

Any participant who is excluded at screening will be replaced by another participant.

4.4 WITHDRAWAL CRITERIA

- Loss of capacity to give informed consent
- Recurrent severe hypoglycaemia
- Terminal illness

Withdrawal will be immediate and subjects will be followed up in the appropriate out-patient diabetes clinic within 4 weeks of withdrawal.

5. ADVERSE EVENTS

5.1 DEFINITIONS

Adverse Event (AE): any untoward medical occurrence in a patient or clinical study subject.

Serious Adverse Event (SAE): any untoward and unexpected medical occurrence or effect that:

- **Results in death**
- **Is life-threatening** – *refers to an event in which the subject was at risk of death at the time of the event; it does not refer to an event which hypothetically might have caused death if it were more severe*
- **Requires hospitalisation, or prolongation of existing inpatients' hospitalisation**
- **Results in persistent or significant disability or incapacity**
- **Is a congenital anomaly or birth defect**

Medical judgement should be exercised in deciding whether an AE is serious in other situations. Important AEs that are not immediately life-threatening or do not result in death or hospitalisation but may jeopardise the subject or may require intervention to prevent one of the other outcomes listed in the definition above, should also be considered serious.

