5.2.1 Non serious AEs

All such events, whether expected or not, should be recorded.

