5.2.2 Serious AEs

An SAE form should be completed and faxed to the Chief Investigator within 24 hours.

All SAEs should be reported to the **<name of REC>** where in the opinion of the Chief Investigator, the event was:

- 'related', ie resulted from the administration of any of the research procedures; and
- 'unexpected', ie an event that is not listed in the protocol as an expected occurrence

Reports of related and unexpected SAEs should be submitted within 15 days of the Chief Investigator becoming aware of the event, using the NRES SAE form for non-IMP studies. The Chief Investigator must also notify the Sponsor of all SAEs.

Local investigators should report any SAEs as required by their Local Research Ethics Committee, Sponsor and/or Research & Development Office.

Contact details for reporting SAEs

Fax: xxx, attention xxx

Please send SAE forms to: xxx

Tel: xxx (Mon to Fri 09.00 – 17.00)

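### Section 5.1 builds 'unexpected' into the SAE definition, so a serious event judged expected can be read as outside the 24-hour form and sponsor notification

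*Combined protocol and SAP*

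**What the plan says.** Section 5.1 of the protocol gives two definitions. An adverse event is "any untoward medical occurrence in a patient or clinical study subject", with no condition on whether it was foreseen. An SAE is "any untoward and unexpected medical occurrence or effect that" has one of five outcomes; the third of these begins "Requires hospitalisation, or prolongation of existing". A closing paragraph allows medical judgement to class other events as serious. It covers "Important AEs that are not immediately life-threatening or do not result in death or hospitalisation but may jeopardise the subject" or may need intervention to prevent a listed outcome.

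The reporting rules follow in section 5.2. Its opening requires every adverse event to be reported and sets no time limit. For non-serious events, section 5.2.1 says: "All such events, whether expected or not, should be recorded". For SAEs, section 5.2.2 sets two duties: "An SAE form should be completed and faxed to the Chief Investigator within 24 hours", and "The Chief Investigator must also notify the Sponsor of all SAEs". It also sends some SAEs to the ethics committee, namely those that are both related to the research procedures and unexpected. The second term is explained there as "ie an event that is not listed in the protocol as an expected occurrence".

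**The concern.** Whether an event is serious depends on its outcome. Whether it is expected depends on whether it was foreseen. The definition in 5.1 merges the two, so an investigator who regards an event as foreseeable has a textual reason not to treat it as an SAE, however grave its outcome.

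The protocol itself foresees severe hypoglycaemia. It is a secondary outcome (section 3.1), a withdrawal criterion when recurrent (section 4.4) and one of the triggers for changing basal rates in the early weeks (section 6, between visits 3 and 4). An admission for severe hypoglycaemia is therefore an event that an investigator could reasonably call expected. What is at stake is whether the Chief Investigator hears of it within 24 hours and whether the sponsor is told.

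**Working it through.** No arithmetic applies and the plan gives no figure to reproduce. The check is to follow one event through the text: a participant is admitted to hospital with severe hypoglycaemia, and the investigator judges this foreseeable in someone starting a pump.

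1. *Is it an adverse event?* Yes. The definition in 5.1 has no expectedness condition.
2. *Is it an SAE?* It meets the hospitalisation outcome, but the opening words of the definition also require it to be unexpected. The answer depends on what that word means in 5.1, where it is not defined and carries no cross-reference.
3. *Does the medical-judgement paragraph bring it back?* Not clearly. That paragraph has no expectedness condition, but its first sentence deals with situations other than the listed outcomes, and its second is worded for events that did not lead to death or hospital admission. Read literally, an expected episode without admission could be classed as serious while an expected episode with admission might not be.
4. *Which duties follow?* Both duties in question, the 24-hour form and the sponsor notification, attach to SAEs only.

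The two available readings of 'unexpected' give different results:

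| Reading of 'unexpected' in 5.1 | SAE? | 24-hour form and sponsor notification | Reported as an adverse event (5.2) |
|---|---|---|---|
| Ordinary sense: not foreseeable | No | Not triggered | Yes, no time limit |
| Explanation in 5.2.2 carried back: not listed in the protocol as expected | Yes, since the protocol has no such list | Triggered | Yes |

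5. *Which reading does the structure support?* Section 5.2.2 selects, from among SAEs, those that are related and unexpected. If 5.1 has already removed every expected event, the second half of that filter has no work to do. The filter makes sense only if SAEs include expected events, which suggests that the condition in 5.1 was not intended. Deleting it makes the two sections agree under either reading.

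**The case against.** The strongest reply is that nothing is excluded in practice. The only explanation of 'unexpected' in the protocol is the one in 5.2.2, and the protocol contains no list of expected occurrences. Naming an event as an outcome or a withdrawal criterion is not the same as listing it as an expected adverse event. On that reading every serious event is unexpected and all of them go on the 24-hour form. This is a fair reading, and it is why the text supports 'can be read as outside' and not 'is outside'. It does not settle the matter, because the explanation is given only for the ethics committee step and 5.1 does not refer to it. How investigators would in fact read 5.1 cannot be known from the documents.

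A second reply is that the medical-judgement paragraph catches severe hypoglycaemia, which section 4.2 defines by the need for help from another person. This stands for episodes without admission and narrows the gap. It does not clearly cover episodes with admission.

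A third is that the trial is small. With 16 participants followed to about day 32 on the pump, exposure is about 16 × 32 = 512 person-days, or 512 / 365 = 1.4 person-years, and section 4.2 admits only people without severe hypoglycaemia in the previous year. The documents give no event rate, so no expected count can be stated, but the number of events affected is likely to be small. That bears on the size of the problem and leaves the contradiction in place.

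A reader might infer more: that a serious but expected event has no reporting route at all, or that the comparison of safety between arms would be incomplete. The documents support neither. Section 5.2 requires every adverse event to be reported, and an event that fails the SAE definition would at the least come under the recording rule in 5.2.1, which applies whether or not it was expected. Severe hypoglycaemia is also a secondary outcome, analysed by intention to treat under section 7, so it is collected in both arms whatever its SAE status. Pump failure, for which section 6 makes provision, adds little as an example: it is a device problem, and becomes a candidate SAE only if it leads to a serious medical event.

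**Conclusion.** The point holds in a limited form. The wording of 5.1 lets a serious event judged expected be treated as not an SAE, and so as outside the 24-hour form and the sponsor notification. It is also at odds with the separate expectedness filter in 5.2.2.

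The effect is on the speed and route of notification. It has no numerical size and does not affect the primary outcome, the sample size or the between-arm data. The conclusion rests on two premises: that 'unexpected' in 5.1 may be given its ordinary meaning, since nothing there says otherwise, and that the medical-judgement paragraph is not clearly written to recover events that led to admission. If the explanation in 5.2.2 were taken to govern 5.1 as well, no event would be excluded and only the redundancy would remain. A 24-hour safety duty should not depend on which reading an investigator chooses, so the change is worth making.

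**What to change.** Delete the words 'and unexpected' from the SAE definition in 5.1, so that seriousness depends on the five listed outcomes and medical judgement. Keep 'related' and 'unexpected' in 5.2.2, where they decide only which SAEs go to the ethics committee. It would help, though it is not essential to this fix, to add the list of expected occurrences to which 5.2.2 refers, so that its filter can be applied as written.

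The cost of the main change is two words in a protocol amendment and possibly a few more SAE forms among 16 participants. No treatment, visit, data item or analysis changes.

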5.2 REPORTING PROCEDURES

All adverse events should be reported. Depending on the nature of the event the reporting procedures below should be followed. Any questions concerning adverse event reporting should be directed to the Chief Investigator in the first instance.

5.2.1 Non serious AEs

All such events, whether expected or not, should be recorded.

5.2.2 Serious AEs

An SAE form should be completed and faxed to the Chief Investigator within 24 hours.

All SAEs should be reported to the **<name of REC>** where in the opinion of the Chief Investigator, the event was:

- 'related', ie resulted from the administration of any of the research procedures; and
- 'unexpected', ie an event that is not listed in the protocol as an expected occurrence

Reports of related and unexpected SAEs should be submitted within 15 days of the Chief Investigator becoming aware of the event, using the NRES SAE form for non-IMP studies. The Chief Investigator must also notify the Sponsor of all SAEs.

Local investigators should report any SAEs as required by their Local Research Ethics Committee, Sponsor and/or Research & Development Office.

Contact details for reporting SAEs

Fax: xxx, attention xxx

Please send SAE forms to: xxx

Tel: xxx (Mon to Fri 09.00 – 17.00)

6. ASSESSMENT AND FOLLOW-UP

Usual pre-pump assessment and screening

Anyone who is being considered for insulin pump therapy will be assessed by their usual care team to complete documentation for funding and to take some blood samples to measure HbA1c, glucose, kidney function, serum C-peptide, coeliac antibodies and thyroid function test. A urine sample will be taken to do a pregnancy test in woman of child bearing age. A medical and medication history will be taken. Validated questionnaires will be used to screen for gastroparesis and hypo unawareness. An insulin pump will be demonstrated and the pros and cons of insulin pump will be explained to ensure a fully informed decision about commencing insulin pump therapy is made. At this appointment potential participants will be provided with a participant information sheet to read in their own time.

At least 24 hours after this appointment potential participants will be contacted to see whether they want to continue with insulin pump therapy, and if so, whether they would like to do this under their usual care team, or under the research team in this trial. This appointment usually takes between 30 and 60 minutes.

Visit 1 - Informed consent - 30 minutes

Following informed consent, participants will be screened as per inclusion and exclusion criteria. This appointment will take up to 30 minutes. Participants will be provided with a capillary blood glucose monitor to use throughout the study if they do not already have one.

Visit 2 – Pre-pump CGM – 60 minutes

Participants will be taught to insert and replace a Dexcom G4 sensor for use with blinded CGM. They will be asked to wear it for one week prior pump initiation, and continuously after pump initiation until the end of the study. Each sensor lasts for 7 days so participants will learn to replace them themselves. They will be asked to keep a food and exercise diary during the pre-pump CGM week, and during week 4 of insulin pump therapy. Participants will be given copies of the data from the CGM at the end of the study. Diabetes self-management will continue as usual. Participants will be asked to complete questionnaires to measure awareness of hypoglycaemia (Gold), hypoglycaemia fear (HFS), general quality of life (WHOQoLBref), diabetes distress (DDS-2) and diabetes quality of life (DQOL), which will be repeated at the end of the study. Self-help leaflets from Diabetes UK will be available in case participants find these questionnaires distressing, and can approach the researcher for signposting for further help. During this session participants will be randomised to a flat basal rate or circadian rate (defined by Roche Accu-Chek software using a predefined algorithm).

Visit 3 – CSII initiation– 3-4 hours

Participants will initiate CSII in pairs from the same randomisation group, at the metabolic day ward in St Mary's hospital on a Monday. They will be taught how to use their insulin pump by a diabetes specialist dietitian trained in insulin pump therapy. They will be asked to take half their usual background insulin the night before, or to exclude the morning dose if they are on twice daily background insulin. Participants will learn to set up the pump, insert the cannula, and learn how to make adjustments to the settings. Both arms will receive half of 75% of their pre-pump total daily insulin dose via basal rates. These basal rates will be calculated in advance ready for programming at the CSII initiation visit.

Participants will receive the research dietitian's contact details for queries in working hours, and will be given a 24 hour product support number in case of pump failure. They will receive

FIRST1D protocol v1.7 23.2.18

IRAS ID: 237129

structured information on what to do manage high and low blood glucose levels. They will be instructed to return to injections in case of pump failure.

Between visits 3 and 4

Participants will be asked to record their blood glucose levels using capillary blood glucose testing a minimum of four times per day – before meals, before bed, and if they feel unwell. These results will be reviewed by the researcher via telephone on day 1, 2 and 4 of pump therapy, and insulin pump settings will be adjusted if needed, based on the criteria below:.

1. Insulin to carbohydrate ratios will be changed by 10% in the event of two values being <4mmol/l within four hours of the meal, or >12mmol/l 4 hours after the meal, in the absence of a precipitating factor
2. Insulin basal rates will only be adjusted in the case of:

- Severe hypoglycaemia
- Recurrent hypoglycaemia (<4mmol/L) at the same time on 3 consecutive days
- Recurrent hyperglycaemia (>12mmol/L) at the same time on 3 consecutive days

The use of temporary basal rates during exercise and activity will be standardised. Participants will be asked to refrain from exercising and using temporary basal rates during the fasting basal rate testing.

Fasting basal rate tests

Participants will undertake a series of fasting basal rate testing commencing on day 7, 14 and 28 of insulin pump therapy. The basal rate testing protocol is as follows:

Day 1 Overnight testing with self-monitoring at 22:00, 00:00, 02:00, 04:00 and 06:00

Day 2 Omit breakfast with self-monitoring at 06:00, 08:00, 10:00: 12:00

Day 3 Omit lunch with self-monitoring at 12:00, 14:00, 16:00, 18:00

Day 4 Omit evening meal with self-monitoring at 18:00, 20:00, 22:00, 00:00, 02:00, 04:00, 06:00

Visit 4 and 5 (Day 11 and 18 of pump therapy)

Insulin pumps and CGM will be downloaded, and insulin basal rates will be adjusted based on the fasting basal rate testing as follows:

- Glucose rise more than 1.7mM during sleep or over a 4 hour period when fasting, increase basal rate by 10% for 2 hours at start of rise
- Glucose fall more than 1.7mM during sleep or over a 4 hour period when fasting, reduce basal rate by 10% for 2 hours at start of fall

Visit 6 (Around day 32 of insulin pump therapy)

Insulin pump and CGM will be downloaded. Participants will be asked to repeat the questionnaires to measure awareness of hypoglycaemia (Gold), hypoglycaemia fear (HFS), general quality of life (WHOQoLBref), diabetes distress (DDS-2) and diabetes quality of life (DQOL). Blood samples to repeat HbA1c will be taken. Pump and CGM downloads will be reviewed, and pump settings adjusted to optimise blood glucose control.

At the end of the study, participants will continue using their insulin pumps if they wish, but will return the CGM. They will be followed up in specialist type 1 insulin pump clinics, as per usual care.

Blood samples will be analysed in the Imperial College Healthcare NHS Trust laboratory and discarded after analysis.

FIRST1D protocol v1.7 23.2.18

IRAS ID: 237129

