Appendix 1. Summary of investigations, treatment and assessments

	Usual pre pump assessment and screening appointment	Informed consent appointment	Pre-randomisation	Days post CSII initiation			
				0	7	14	28
Informed consent		X					
Blood tests (Thyroid function tests, coeliac serology, plasma glucose, serum c-peptide)	X						X
HbA1c (blood test)	X						X
GOLD score questionnaire	X						X
Blinded CGM			X	X	X	X	X
Psychosocial questionnaires			X				X
Basal rate testing					X	X	X
Pump download					X	X	X

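### Does starting pumps in same-arm pairs, with a pre-pump week labelled pre-randomisation although allocation is at Visit 2, call for a change to the plan?

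*Combined protocol and SAP*

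**What the plan says.** Section 6, Visit 2, starts blinded continuous glucose monitoring: "They will be asked to wear it for one week prior pump initiation". It then describes the questionnaires and ends with allocation: "During this session participants will be randomised to a flat basal rate or circadian rate". For Visit 3, a shared session of 3 to 4 hours held on a Monday, it states "Participants will initiate CSII in pairs from the same randomisation group". The starting rates come from the dose before the pump: "Both arms will receive half of 75% of their pre-pump total daily insulin dose via basal rates".

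Two other places name the lead-in week differently. The Study Summary gives the duration as "4 weeks plus 1 week pre-randomisation assessment", and section 3 has "4 week trial with 1 week pre-randomisation assessment". Appendix 1 heads a column "Pre-randomisation", with blinded monitoring and the psychosocial questionnaires ticked beneath it.

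The only replacement rule is in section 4.3: "Any participant who is excluded at screening will be replaced by another participant". Section 7 compares the arms by a two-sided independent t test on individuals, under intention to treat and with available data only. It calls the study a pilot. No rule is given for forming pairs, for someone left without a partner, or for counting the shared session in healthcare professional time.

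**The concern.** If allocation takes place at Visit 2, the week described as preceding randomisation in fact follows it. The monitoring data and diary would then not be a true pre-allocation baseline. The pre-pump total daily dose might not be either, if it is read from that week. That dose fixes the starting basal rate, which is the reference point of the primary outcome.

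Pairing adds to this. Individual randomisation does not deliver same-arm partners on the same Monday, so someone may be held, and one loss before Visit 3 can leave an arm with an odd number. People trained together may also have correlated outcomes, which an independent t test ignores. At stake would be the validity of the baseline, the standard error of the primary comparison, and the meaning of staff time as a secondary outcome.

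**Working it through.** **Timing.** The firm conflict is between section 6 and the duration lines in the Study Summary and section 3. Appendix 1 has a column heading and names no week. Since Visit 2 describes the questionnaires before allocation, that column can be read as Visit 2 up to the moment of allocation. The possible routes from the slip to a result are:

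- Monitoring data: the device is blinded, participants see their data only when the study ends, and self-management is unchanged. Section 7 plans no adjustment for baseline monitoring.
- Primary outcome: its baseline is a pump basal rate, reached only through the pre-pump total daily dose. Section 6 does not say when that dose is recorded, but a medication history is taken at the usual pre-pump assessment, before consent. The same conversion applies in both arms.
- Analysis set: someone who never starts a pump has no basal-rate change, so under the available-data rule they add nothing to the t test whichever time of allocation is meant.

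**Forming pairs.** Section 3 gives 16 participants at 1:1, so 8 per arm and 4 pairs per arm. On an unblocked 8:8 list (assumed), two people ready together share an arm with probability 7/15 = 0.467 and differ with probability 8/15 = 0.533. A differing twosome does not always mean a wait. If people come two at a time, the first differing twosome leaves one person waiting in each arm, the next supplies both partners, and so on alternately. A wait is therefore forced in half of them: 0.533/2 = 0.267, or about 27% of twosomes.

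With no co-ordinated booking, random arrivals and pairing in enrolment order, the mean gap between same-arm partners is 17/9 places on the list. Section 7 reports 47 pump starts in a year. If all enrolled, the mean hold is (17/9)/(47/52) = 2.1 weeks; at half that rate it is 4.2 weeks. Booking Visit 2 in fours, allocated 2:2, makes it zero. Visit 3 is a planned appointment, so the result depends mainly on booking, and both arms face the same rule.

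**Odd arms.** With loss p per person between Visits 2 and 3 (assumed), an arm of 8 loses an odd number with probability q = [1 − (1 − 2p)^8]/2, and at least one arm is odd with probability 1 − (1 − q)². For p = 2%, 5% and 10% this is 26%, 49% and 66%. The practical result is one person starting alone.

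**Primary test.** The plan states no significance level, effect size, SD or power, so there is no figure of its own to reproduce. Assume 5% two-sided and a within-pair correlation (ICC) of 0.05 or 0.1.

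- The standard error is too small by 1 − √{[(7 − ICC)/7]/(1 + ICC)} = 2.8% and 5.3%.
- Simulated size of the individual t test is 5.6% and 6.2%.
- Power at 1.507 SD with no clustering is 80% for the individual test (14 df, critical value 2.145) and 71% for a test on pair means (6 df, 2.447). At ICC 0.1 the pair-mean test has 67%.
- Among significant individual-level results at that difference, the pair-mean test is not significant in 14.2% at ICC 0 and 17.6% at ICC 0.1 (400,000 simulated trials each). Most disagreements would reflect the loss of degrees of freedom.

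**Staff time.** Visits 1 to 3 total 0.5 + 1 + (3 to 4) = 4.5 to 5.5 h if Visit 3 is credited in full, or 0.5 + 1 + (1.5 to 2) = 3.0 to 3.5 h if halved. With everyone paired, this cancels between arms. Under halving, one lone starter in an arm of seven raises that arm's mean by 1.5/7 to 2/7 = 0.21 to 0.29 h.

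**The case for a change.** The best case for acting is that two statements about the time of allocation cannot both be true, and a reader is entitled to know whether a baseline precedes allocation. A lone starter is foreseeable even at modest loss rates, and the only replacement rule covers exclusion at screening. The remedy would cost little: some wording and one extra analysis, with the primary test untouched. If pairs were the unit randomised, the individual t test would be the wrong primary analysis.

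The conflict of labels and the silence on pairing both stand. The rest does not carry a change. Section 3 and the Visit 2 text allocate participants, not pairs, so the individual is the unit. Intention to treat already keeps a lone starter in the allocated arm, and section 8.2 keeps people given alternative treatment in follow-up and analysis. No direction of bias can be named. A larger ICC would matter more: size reaches 7.5% at 0.2 and 11.8% at 0.5. Values that high are hard to credit here, because basal rates are changed according to each person's own glucose readings and fasting tests.

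**Conclusion.** No change follows. Naming the week pre-randomisation is a clerical slip that alters no comparison. The rules for pairing, a lone starter and crediting the shared session are details that a single site and its analysts fill sensibly and equally in both arms. The pair-mean test offers no real gain: it gives up 9 percentage points of power (80% to 71%) where there is no clustering, to guard against a size of 5.6% to 6.2% in a declared pilot, and it could hardly tell pairing from lost degrees of freedom.

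This rests on a 5% two-sided level, an ICC of no more than about 0.1, and allocation of individuals as the text says. The waiting times and odd-arm rates depend on assumed arrivals and losses, and they show inconvenience, not bias. The one loose end is the pre-pump dose: if it were read from the week after allocation, the baseline would technically follow allocation, but the documents do not say so and the same conversion is used in both arms.
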